1.2.2 Clinical Safety Background

To date, MHAA4549A has been shown to be safe and well tolerated in three *completed* clinical studies, which altogether enrolled 136 healthy volunteers. In addition, *an ongoing global Phase 2b Study (GV29216), in 24 countries across North America, Europe, Latin America, and Asia-Pacific, is currently enrolling hospitalized patients with severe influenza infection and has shown no clinically significant drug-related safety signals.*

1.2.2.1 Phase 1 Entry-into-Human Study (GV28916)

In the Phase 1 entry-into-human (EIH) study (GV28916), 21 healthy volunteers were given single IV doses of placebo or MHAA4549A at 1.5 mg/kg, 5 mg/kg, 15 mg/kg, or 45 mg/kg and followed for 120 days.

A total of 23 treatment emergent adverse events (TEAEs) were reported by 13 of the 21 subjects (61.9%) who received one dose of the study medication. Nineteen of these TEAEs were reported by 10 of the 16 subjects (62.5%) who had received MHAA4549A and 4 TEAEs were reported by 3 of the 5 subjects (60.0%) who received placebo. The total number of TEAEs reported was similar in all dosing cohorts (4 TEAEs per cohort), with the exception of the 5 mg/kg cohort, where seven TEAEs were observed. Overall, no notable trends were observed among dose levels or between subjects who received MHAA4549A versus placebo.

The most commonly reported TEAEs in subjects receiving MHAA4549A were headache (4 subjects) and oropharyngeal pain (2 subjects). The severity of TEAEs was primarily mild, with only two moderate TEAEs. No serious adverse events or dose-limiting toxicities were reported. Two clinical laboratory values were considered TEAEs (an increase in ALT in one subject who received 5 mg/kg MHAA4549A and an increase in creatinine phosphokinase [CK] in 1 subject who received placebo). Both results returned to normal within 10 days.

No safety issues were observed with respect to vital signs or ECG measurements. Overall, no relevant differences in mean values or deviations from baseline over time were observed in subjects receiving MHAA4549A as compared to placebo for all lab values. No *drug-emergent* anti-therapeutic antibodies (ATAs) were detected in this study.

1.2.2.2 Phase 1 High-Dose Safety Study (GV29609)

In the Phase 1 high-dose Study (GV29609) 14 healthy volunteers were given single IV doses of placebo or MHAA4549A at 8400 mg (*Cohort A*) or 10800 mg (*Cohort B*) and followed for 120 days.

A total of 34 TEAEs were reported by 12 (85.7%) of the 14 subjects who received one dose of the study medication or placebo (safety population). Twenty-four (24) of these TEAEs were reported by 7 (87.5%) of the 8 subjects who had received MHAA4549A

and 10 TEAEs were reported by 5 (83.3%) of the 6 subjects who received placebo. TEAEs were reported by 3 of the 4 subjects receiving 8,400 mg MHAA4549A and 4 of 4 subjects receiving 10,800 mg MHAA4549A. No notable trends in types of TEAEs or laboratory results were observed between dose levels or between subjects who received MHAA4549A versus placebo.

The most commonly reported TEAEs were headache, reported by 4 subjects who received MHAA4549A (3 subjects in Cohort A and 1 subject in Cohort B), and nasopharyngitis, reported by three subjects who received MHAA4549A (1 subject in Cohort A and 2 subjects in Cohort B). All other TEAEs were each reported by no more than 1 subject who received MHAA4549A. The severity of TEAEs was primarily mild, with only three moderate TEAEs reported (a bacterial infection, observed in one subject who received 8400 mg MHAA4549A, and elevations of blood CK, observed twice in one subject who received 10,800 mg MHAA4549A). No serious adverse events or dose-limiting toxicities were reported.

No safety issues were observed with respect to vital sign results and ECG measurements. Overall, no relevant differences in mean values and changes or shifts from baseline over time were observed with respect to dose levels or MHAA4549A compared to placebo. No subjects in the study developed an ATA response following study drug administration.

1.2.2.3 Phase 2a Influenza Nasal Challenge Study (GV28985)

In the Phase 2a challenge Study (GV28985), 101 healthy volunteers were nasally inoculated with the H3N2 (A/Wisconsin/67/2005) strain of influenza virus. At 24–36 hours after inoculation, 60 subjects received single IV doses of 400 mg, 1200 mg, or 3600 mg MHAA4549A, 8 subjects received oseltamivir as an active comparator, and 32 subjects received placebo. All subjects, regardless of initial treatment, received oseltamivir on Days 7–11 to mitigate risk of late shedding and/or further transmission of virus.

Adverse events were collected from time of influenza A inoculation (Day 0). There was no evidence of a dose-related pattern of TEAEs in MHAA4549A-treated subjects, an observation that is consistent with *all of* the Phase 1 studies (GV28916 and GV29609) *conducted to date*. Expected influenza-related symptoms and adverse events were observed in inoculated subjects; these influenza-related adverse events were similar in subjects who received MHAA4549A or placebo. Of the 101 subjects randomized, 23 subjects experienced at least 1 adverse event following virus inoculation but prior to the first dose of study medication. The most common adverse events seen prior to the administration of study drug were headache (4 subjects), elevated blood pressure (4 subjects), dizziness (3 subjects), and procedural hemorrhage (3 subjects).

Following administration of the study drug, there were 207 TEAEs in 86 of the 100 safety evaluable subjects (86%) that occurred in a similar pattern across all treatment groups.

Thirty-six of the 86 subjects (42%) experienced ≥ 1 study-drug related TEAE. Study-drug related TEAEs occurred in a similar proportion and in a similar pattern across all treatment groups. The most common TEAEs were elevations in ALT, AST, and amylase which were reported in 15 of 25 TEAEs (60%) in subjects receiving placebo (n=32) or oseltamivir (n=8) and 26 of 33 TEAEs (79%) in subjects receiving MHAA4549A (n=60). Similar elevations have been seen previously following influenza infection (Polakos et al. 2006; Yingying 2011). There were no clinically significant changes in vital signs, spirometry, or electrocardiograms, and no pattern of study drug-related effects in these parameters. There were no observed adverse events or safety events that were considered attributable to interactions between oseltamivir and MHAA4549A.

1.2.3 Clinical Pharmacokinetics

The Phase 1 EIH study (GV28916) demonstrated that MHAA4549A serum pharmacokinetics (PK) was dose proportional with a mean half-life of approximately 23 days (range: 21.9 to 24.6 days). The PK profile appeared consistent with that of a human IgG1 antibody that lacks known endogenous host targets (Ishida et al. 2015).

In the Phase 2a influenza nasal challenge study (GV28985), serum MHAA4549A concentrations exhibited a biphasic disposition with an initial rapid distribution phase followed by a slow elimination phase, which was also observed in the Phase 1 EIH study (GV28916). MHAA4549A demonstrated linear *serum* PK. The group mean maximum observed concentration (C_{max}) increased in a dose-proportional manner of 116 $\mu\text{g/mL}$ for the 400-mg dose group and 1110 $\mu\text{g/mL}$ for the 3600-mg dose group. Similarly, the group mean area under the curve from zero to infinity ($AUC_{0-\infty}$) was 1800 and 18,100 $\text{day} \cdot \mu\text{g/mL}$ for the 400- and 3600-mg dose groups, respectively, and is approximately dose proportional. PK data from the Phase 2a study (GV28985) is consistent with that observed in the Phase 1 study (GV28916), with MHAA4549A demonstrating a mean half-life of approximately 23 days (mean range: 22.5–23.7 days).

In the Phase 1 high-dose study (GV29609), MHAA4549A showed serum linear PK with a mean half-life ($t_{1/2}$) of approximately 21.5 days (range 21.4–21.6 days). For the 8,400-mg and 10,800-mg dose groups, the mean apparent clearance (CL) and the mean

volume of distribution at steady state (V_{ss}) ranged from 151 to 167 mL/day and from 4590 to 4170 mL, respectively. PK data from the Phase 1 high dose study (GV29609) are consistent with that observed in the Phase 1 study (GV28916) and Phase 2a study (GV28985).

1.2.4 Clinical Efficacy Background

The virologic efficacy analysis for the Phase 2a challenge study (GV28985), presented in [Table 1](#), includes the Intent-to-Treat infected (ITTI) population who received 400 mg MHAA4549A (N=11), 1200 mg MHAA4549A (N=13), 3600 mg MHAA4549A (N=14), oseltamivir alone (N=2), or placebo (N=21). The ITTI population included all subjects who were randomized, inoculated with challenge virus, and had laboratory confirmed evidence of influenza infection as defined by one or more of the following:

- A positive cell culture assay by 50% tissue culture infectious dose (TCID₅₀) at least once during quarantine post-challenge virus inoculation
- Or
- At least two positive detections by any qPCR assay between virus inoculation and day of discharge from quarantine
- Or
- Seroconversion (≥ 4 -fold rise in titer compared to baseline)

1.2.4.1 Virologic Efficacy

The 400-mg dose demonstrated a decrease in viral shedding (reduction in median viral area under the curve (AUC) by quantitative polymerase chain reaction [qPCR]) by 46% ($p=0.05$) and peak viral load (reduction in median peak viral load by qPCR) by 20.4% ($p=0.02$). The 1200-mg dose showed a decrease in viral shedding by 3.0% ($p=0.90$) and peak viral load by 0.3% ($p=1.00$). The 3600-mg dose level demonstrated a significant decrease in viral shedding by 97.5% ($p=0.01$) and peak viral load by 77.3% ($p=0.002$) ([Table 1](#)). The decreased efficacy observed in the 1200-mg dose group is thought to be due to variability from the challenge model and inter-subject differences.

1.2.4.2 Symptomatic Efficacy

The A/Wisconsin/67/2005 virus induced mild symptoms that were predominantly limited to the upper respiratory tract, including rhinorrhea, nasal congestion, and sneezing. Duration and severity of influenza-related symptoms (rhinorrhea, nasal congestion, sneezing, sore throat, earache, malaise, cough, shortness of breath, headache, and muscle/joint ache) were collected on a self-reported Symptom Diary Card. The cards grade the symptoms on a scale of 0–3, where Grade 0 is absence, Grade 1 is just noticeable, Grade 2 is bothersome but does not prevent participation in activities, and Grade 3 is bothersome and interferes with activities. Composite clinical symptom scores for the ITTI population are shown in [Table 1](#).

Consistent with the virological results, there was a trend toward a decrease in the symptoms scores for the 3600-mg dose with a mean reduction of the composite symptom score of 82% (Table 1).

Table 1 GV28985 Efficacy Results from Intent-to-Treat Infected Population

Endpoint	MHAA4549A				
	Placebo (N=21)	400 mg (N= 11) % Reduction (p-value)	1200 mg (N= 13) % Reduction (p-value)	3600 mg (N= 14) % Reduction (p-value)	Oseltamivir (N=2) % Reduction (p-value)
Median qPCR AUC (log ₁₀ vc/mLxhour)	458.1	247.2 46.0% (0.0455)	444.4 3.0% (0.9020)	11.3 97.5% (0.0051)	57.4 87.5% (0.0558)
Median Cell Culture AUC (log ₁₀ TCID ₅₀ × hour)	186.8	70.3 62.4% (0.0087)	224.5 -20.2% (0.8742)	0.0 100% (0.0023)	28.8 84.6% (0.0558)
Median qPCR Peak (log ₁₀ vc/mL)	6.38	5.08 20.4% (0.0187)	6.36 0.3% (1.0000)	1.45 77.3% (0.0024)	2.30 63.9% (0.0947)
Median Cell Culture Peak (log ₁₀ TCID ₅₀)	4.25	1.75 58.8% (0.0220)	4.00 5.9% (0.9578)	0.00 100% (0.0023)	1.25 70.6% (0.1150)
Median Composite Symptom Score AUC	207.7	87.5 57.9% (0.2000)	192.1 7.5% (0.8743)	37.7 81.8% (0.2887)	8.1 96.1% (0.0855)

AUC=area under the curve; mg=milligram; mL=milliliter; qPCR=quantitative polymerase chain reaction; vc=viral copies; TCID₅₀=50% tissue culture infectious dose.

Note: Comparison of 400 mg, 1200 mg, 3600 mg and oseltamivir to placebo using nonparametric Wilcoxon rank-sum test. % Reduction is calculated as 100%*[(the median of placebo – the median of active)/the median of placebo]. All p-values are unadjusted for multiple testing.

The responses observed in the Phase 2a study (GV28985) suggest that higher doses of MHAA4549A may improve virological and symptomatic efficacy in a population with influenza infection. Because of this, an 8400-mg dose will be assessed in this study.

1.3 STUDY RATIONALE AND BENEFIT-RISK ASSESSMENT

Two Phase 1 (GV28916, GV29609) studies have demonstrated that MHAA4549A is safe and well tolerated in healthy volunteers at doses up to 10800 mg. Data from the Phase 2a study (GV28985) demonstrated that doses of approximately 3600 mg MHAA4549A are safe, well tolerated, and effective in reducing viral titers and influenza symptoms as compared to placebo in healthy volunteers inoculated with influenza A

virus. No MHAA4549A-specific TEAEs have been identified in any of our clinical studies. When combined with nonclinical studies demonstrating that MHAA4549A has a well-tolerated safety profile and in vitro and in vivo efficacy against influenza virus, these findings support further clinical development of MHAA4549A.

The primary goal of this exploratory Phase 2 Study (GV29893) is to demonstrate safety and tolerability of MHAA4549A in otherwise healthy patients with naturally *acquired* acute uncomplicated seasonal influenza A. The study will also assess the potential ability of MHAA4549A to reduce the severity and/or duration of clinical signs and symptoms, [REDACTED] related to acute *uncomplicated* influenza. Other measures, such as influenza reinfection rate, frequency of secondary complications, hospital admissions, mortality, *PK, immunogenicity, and biomarkers* will also be assessed.

Potential risks of MHAA4549A include immunogenicity and infusion-related reactions. Theoretically, any biological agent may evoke these responses. To date, MHAA4549A has not been associated with the development of allergic or anaphylactic reactions or infusion-related reactions in preclinical or clinical studies. *In the three clinical trials conducted so far, none of the subjects dosed with MHAA4549A developed an ATA response.* No adverse events have been identified that are specific to MHAA4549A.

Antibody-dependent enhancement (ADE) of *disease* has been suggested as a potential risk of antiviral antibodies *when used* as therapeutic interventions for influenza (Khurana et al. 2013). ADE of *infection* might occur when non-neutralizing antiviral antibodies facilitate virus entry into host cells, leading to enhanced viral replication *and shedding* (Takada and Kawaoka 2003; Whitehead et al. 2007; Dejnirattisai et al. 2010; Crowe 2013). In the Phase 2a challenge study (GV28985), no signs or symptoms of ADE were observed, including higher viral titers/genomes or increases in clinical symptom scores in subjects receiving MHAA4549A as compared to placebo.

2. OBJECTIVES

2.1 PRIMARY OBJECTIVE

- To evaluate the safety and tolerability of a single IV dose of MHAA4549A as compared to placebo when administered in otherwise healthy patients with acute uncomplicated seasonal influenza A, focusing on the following:

Nature, frequency, and severity of serious and non-serious adverse events

Effects on laboratory values, vital signs, ECG parameters, and other safety biomarkers

2.2 SECONDARY OBJECTIVES

- To examine the time to alleviation of clinical signs and symptoms of influenza A infection
- To examine the severity of clinical signs and symptoms of influenza A infection

- To measure hospital admission rate
- *To measure duration of hospital stay*
- To measure antibiotic usage for secondary bacterial respiratory infections
- To measure the frequency, severity and development of secondary complications of influenza (pneumonia, exacerbation of chronic lung disease, myocarditis, acute respiratory distress syndrome, acute otitis media, other related complications)
- *To measure the incidence of death*
- To measure influenza re-infection rate

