3.4.2 Secondary Outcome Measures

- Time to alleviation of all symptoms (nasal congestion, sore throat, cough, aches, fatigue, headaches, chills/sweats) with resolution maintained for 24 hours (without use of symptom relief medications) as defined by a rating 0 (none) or 1 (mild) for each symptom on a 4-point scale of 0–3. For patients who enroll with mild symptoms, the symptom score must be reduced by 1 point during the study duration.
- Incidence of reinfection or relapse with influenza at 100 days after end of treatment
- Incidence of hospitalization for influenza-related complications at 100 days after end of treatment and length of stay
- Antibiotic usage for secondary bacterial respiratory infections
- Incidence of complications of influenza (e.g., pneumonia, exacerbations of chronic lung disease, myocarditis, acute respiratory distress syndrome (ARDS), otitis media, or other influenza related complications)
- *Incidence of death*

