5.3.5.8 Deaths

Deaths that occur during the protocol-specified adverse event reporting period (see Section 5.3.1) that are attributed by the investigator solely to progression of influenza or any related co-morbidities should be recorded only on the Study Completion/Early Discontinuation eCRF. All other on-study deaths, regardless of relationship to study drug, must be recorded on the Adverse Event eCRF and immediately reported to the Sponsor (see Section 5.4.2).

Death should be considered an outcome and not a distinct event. The event or condition that caused or contributed to the fatal outcome should be recorded as the single medical concept on the Adverse Event eCRF. Generally, only one such event should be

reported. The term "**sudden death**" should be used only for the occurrence of an abrupt and unexpected death due to presumed cardiac causes in a patient with or without pre-existing heart disease, within 1 hour after the onset of acute symptoms or, in the case of an unwitnessed death, within 24 hours after the patient was last seen alive and stable. If the cause of death is unknown and cannot be ascertained at the time of reporting, "**unexplained death**" should be recorded on the Adverse Event eCRF. If the cause of death later becomes available (e.g., after autopsy), "unexplained death" should be replaced by the established cause of death.

Deaths that occur after the adverse event reporting period should be reported as described in Section 5.6.

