6.4 PRIMARY SAFETY ANALYSES

The safety analyses will include all randomized patients who received study drug, with patients grouped according to the treatment actually received. Safety parameters to be evaluated include adverse events (including deaths, serious adverse events, discontinuations due to adverse events, and the incidence and severity of adverse events), clinical laboratory tests, vital signs, and ECGs. All collected adverse event data will be listed by study site and patient number. All adverse events that occur on or after treatment on Day 1 will be summarized for each treatment group by mapped term, appropriate thesaurus levels, body system, and event within each body system, and toxicity grade. In addition, all serious adverse events, including deaths, will be listed separately and summarized. Serious adverse events caused by a protocol-mandated intervention (e.g., invasive procedures such as biopsies, discontinuation of medications) that occur between consent and first dose of study medication will be listed separately.

Laboratory data with values outside of the normal ranges will be identified. In addition, select laboratory data will be summarized by treatment group using descriptive summary statistics.

The absolute and percentage changes from baseline in vital sign parameters will be computed, and changes deemed clinically significant by the Investigator will be noted. Appropriate descriptive summary statistics will be provided for all vital sign parameters.

The prevalence (baseline) of ATA will be reported and correlation with PK, safety, efficacy, and *biomarker* endpoints will be analyzed as data allow.

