6.5 SECONDARY EFFICACY ANALYSES

The efficacy analyses will include all randomized patients who are confirmed to be influenza A infected, with patients grouped according to the treatment assigned at randomization. Efficacy parameters to be evaluated include duration and severity of influenza symptoms, hospitalization, and influenza-related complications.

Time to event data will be analyzed using Kaplan-Meier methodology and will be summarized using n, median when estimable, hazard ratios, and 95% confidence intervals. Patients who are lost to follow-up (while event free) will be censored at the time that they are last known to be event free.

Estimation of the treatment difference of proportions and its 95% confidence interval will be calculated using stratum-adjusted Mantel-Haenszel methodology ([Koch et al. 1989](#)). For continuous endpoints, Analysis of Covariance methods (after appropriate transformation of data) will be used to estimate treatment differences and 95% confidence intervals.

Other than censoring in the time to event analyses, no other imputation for missing data will be performed.

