6.5.1 Secondary Endpoints

- Median time to alleviation of clinical signs and symptoms of influenza A infection
- Proportion of patients requiring hospitalization
- Median duration of hospitalization
- Proportion of patients with influenza-related deaths
- Proportion of patients requiring antibiotics for respiratory infection
- Proportion of patients with influenza secondary complications
- Proportion of patients with influenza re-infection

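### The death objective and outcome carry no cause restriction, but the only death endpoint is influenza-related death in confirmed patients, and the safety summary may miss influenza-only deaths

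*Combined protocol and SAP*

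**What the plan says.** Five places in the combined protocol and SAP bear on this.

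- **Objective and outcome.** Section 2.2 has "To measure the incidence of death"; Section 3.4.2 has "Incidence of death". Neither names a cause. The same list in 3.4.2 does limit hospitalization to influenza-related complications.
- **Analysed endpoint.** Section 6.5.1 has "Proportion of patients with influenza-related deaths", and no other death endpoint.
- **Population for that endpoint.** Section 6.5: "The efficacy analyses will include all randomized patients who are confirmed to be influenza A infected", grouped as randomized. Section 6 makes the confirmation a central PCR on Day 1 pre-dose samples.
- **Recording of deaths.** Under Section 5.3.5.8, deaths that the investigator attributes "solely to progression of influenza or any related co-morbidities should be recorded only on the Study Completion/Early Discontinuation eCRF". For the rest: "All other on-study deaths, regardless of relationship to study drug, must be recorded on the Adverse Event eCRF".
- **Safety analysis.** Section 6.4 covers all randomized patients who received study drug, grouped by treatment received. It states "Safety parameters to be evaluated include adverse events (including deaths, serious adverse events, discontinuations due to adverse events", and later "In addition, all serious adverse events, including deaths, will be listed separately and summarized". It does not say whether deaths recorded only on the completion form are brought in.

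**The concern.** A secondary objective about death as such is answered by an endpoint about one class of death in a subset of patients. The remaining deaths are left to a safety summary whose natural data source, the Adverse Event eCRF, excludes another class by rule. Deaths are thus divided by attribution between two analyses that differ in data source, population and grouping.

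The dividing line is a judgment about cause, and it falls where the protocol sees a possible risk. Section 1.3 discusses antibody-dependent enhancement of influenza disease. A death from enhanced disease could be judged to be influenza progression and so stay off the Adverse Event eCRF. Section 5.3.5.10 does ask for unexpected worsening to be recorded as an adverse event, so the route depends on whether the investigator calls the course unexpected. A count of deaths from any cause, by arm, needs no such judgment. With very few deaths likely, where one case is counted could be the whole comparison.

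**Working it through.** The plan gives no figure for deaths, so there is none to reproduce. Table 5 concerns adverse events with 40 patients per arm and does not bear on this point. The check is to trace each kind of death through the rules.

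**Step 1: kinds of death.** Cause is taken as solely influenza (including related co-morbidities), influenza-related but not solely so, or unrelated. Each can occur in a patient who is or is not confirmed by central PCR: 3 × 2 = 6 types.

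**Step 2: rules.** The 6.5.1 endpoint counts a death if the patient is confirmed and the death is influenza-related, solely or in part. A 6.4 summary built on the Adverse Event eCRF counts a death in a dosed patient unless it is attributed solely to influenza.

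**Step 3: result.**

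| Cause of death | Central PCR | 6.5.1 endpoint | 6.4 from Adverse Event eCRF |
|---|---|---|---|
| Solely influenza | confirmed | counted | missed |
| Solely influenza | not confirmed | missed | missed |
| Influenza-related, not solely | confirmed | counted | counted |
| Influenza-related, not solely | not confirmed | missed | counted |
| Unrelated | confirmed | missed | counted |
| Unrelated | not confirmed | missed | counted |

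The 6.5.1 endpoint counts 2 of 6 types and the Adverse Event eCRF summary 4 of 6. One type is in both, so together they reach 2 + 4 − 1 = 5 of 6. The missing type is an influenza-only death in a patient not confirmed by central PCR. The type in both is an influenza-related but not solely influenza death in a confirmed patient. The all-cause count therefore cannot be obtained by adding the two results. The different groupings, as randomized and as treated, are a further obstacle.

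**Step 4: how often this could matter.** The documents give no death rate. Assuming a risk per patient of 0.1% to 1%, the expected number of deaths among 141 patients is 141 × 0.001 = 0.14 to 141 × 0.01 = 1.4. The chance of at least one is 1 − 0.999^141 = 13% to 1 − 0.99^141 = 76%. The upper end is a generous assumption for otherwise healthy adults aged 18 to 65 with uncomplicated influenza.

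**The case against.** The strongest reply is that the safety analysis already does the work. Section 6.4 names deaths, covers all dosed patients and sets no cause restriction. Section 6.2 lists and summarizes reasons for early termination by arm, and the completion form is where influenza-only deaths are recorded, so that table could show every death. Section 5.2.2 makes any fatal adverse event serious, with no exception for influenza. Section 5.3.5.10 sends unexpected worsening to the Adverse Event eCRF, and in this healthy population a fatal course would plausibly be called unexpected. An influenza-only death in a confirmed patient is counted in 6.5.1 anyway. The trial does no formal testing.

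Much of this stands, and it rules out three stronger readings.

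- A reader might infer that no planned analysis counts all deaths. The documents do not support that: 6.4 plans a listing and summary of deaths, and 6.2 could display them all if death is a reason category, although the plan does not say that it is.
- A reader might infer that a death from a drug reaction would go unreported. It would not. Section 5.3.5.8 puts every death not attributed solely to influenza or related co-morbidities on the Adverse Event eCRF, and 6.4 summarizes it. It is absent only from the 6.5.1 line.
- A reader might infer that the investigator decides what counts as influenza-related in 6.5.1. That section names no one and gives no rule; 5.3.5.8 uses investigator attribution only to choose the form.

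It is also true that the phrase any cause is not in the plan. It is the natural reading of unqualified wording, supported by 3.4.2 limiting cause for hospitalization but not for death.

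The reply does not remove the mismatch between 2.2 and 3.4.2 on one side and 6.5.1 on the other. Nor does it show that 6.4 takes in deaths recorded only on the completion form.

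**Conclusion.** The concern holds in a limited form. As written, the endpoint in 6.5.1 does not deliver the objective in 2.2 or the outcome measure in 3.4.2. No all-cause death proportion by arm is specified, and the death summary in 6.4 would miss influenza-only deaths unless completion-form deaths are added. The two analyses together still leave out one of six types of death and count one twice.

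This assumes that unqualified death means death from any cause, that the 6.4 summary is built from the Adverse Event eCRF, and that deaths due solely to influenza count as influenza-related in 6.5.1. If the sponsor already intends to merge the two forms for 6.4, that part becomes a matter of saying so; the mismatch with 6.5.1 remains.

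The practical effect is small. Every death is recorded on one form or the other, deaths should be rare, and sample size and the other analyses are unaffected. The summary of changes shows death being added to the objectives and outcome measures and lists no change to 6.5.1. An edit not carried through is a likely explanation, though not a proven one.

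**What to change.** 1. In 6.5.1, specify the proportion of patients who died from any cause through Day 100, by arm, derived from the Study Completion/Early Discontinuation and Adverse Event eCRFs combined, counting each patient once. Show it for all dosed patients and for the confirmed-infected set.
2. Keep influenza-related death as a descriptive breakdown of that count, with a stated rule for who attributes the cause and how.
3. In 6.4, state that deaths recorded only on the completion form are included in the death listing and summary, and reconcile this with 5.2.2 and 5.3.5.8.

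The cost is one endpoint line, one derived variable, a short attribution rule and one sentence in 6.4. Both forms are already collected, so no patients, visits or data are added.
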